Chest pain Acute chest pain (finding) Atypical chest pain (finding) Cardiac chest pain (finding) Central chest pain (finding) Chest pain at rest (finding) Chest pain due to pericarditis (finding) Chest pain on breathing (finding) Chest pain on exertion (finding) Chest wall pain (finding) Crushing chest pain (finding) Dull chest pain (finding) Ischemic chest pain (finding) Left sided chest pain (finding) Localized chest pain (finding) Musculoskeletal chest pain (finding) Noncardiac chest pain (finding) Parasternal pain (finding) Pleuritic pain (finding) Pleuropericardial chest pain (finding) Precordial pain (finding) Radiating chest pain (finding) Retrosternal pain (finding)	SCTID: 29857009 SCTID: 102587001 SCTID: 102589003 SCTID: 426396005 SCTID: 161972006 SCTID: 9267009 SCTID: 34791000119103 SCTID: 274664007 SCTID: 81953000 SCTID: 102588006 SCTID: 59139008 SCTID: 3368006 SCTID: 225566008 SCTID: 285385002 SCTID: 97001000119106 SCTID: 281245003 SCTID: 274668005 SCTID: 161974007 SCTID: 2237002 SCTID: 13057000 SCTID: 71884009 SCTID: 10000006 SCTID: 4568003

Table 3 SNOMED-CT concepts for the study	
Study outcome	SNOMED code
Right sided chest pain (finding)	SCTID: 285386001
Squeezing chest pain (finding)	SCTID: 371030007
Upper chest pain (finding)	SCTID: 285389008
Angina decubitus (disorder)	SCTID: 59021001
Angina (disorder)	SCTID: 194828000
(Prevalent) History of angina pectoris (situation)	SCTID: 161504004
Gait disturbances	
Abnormal gait (finding)	SCTID: 22325002
Tandem gait test - abnormal (finding)	SCTID: 401211005
Functional gait abnormality (finding)	SCTID: 69161000119103
Abnormal gait due to muscle weakness (finding)	SCTID: 432559006
Abnormal gait due to impairment of balance (finding)	SCTID: 431524008
Frontal gait disorder (disorder)	SCTID: 250054005
Peripheral sensory gait disorder (finding)	SCTID: 250027007
High level sensorimotor gait disorder (finding)	SCTID: 250043000
Low level sensorimotor gait disorder (finding)	SCTID: 250003005
Middle level sensorimotor gait disorder (finding)	SCTID: 250034009
Peripheral skeletomuscular gait disorder (finding)	SCTID: 250004004
Ataxic gait (finding)	SCTID: 25136009
On examination - gait ataxic (finding)	SCTID: 163686004
Visual ataxic gait (finding)	SCTID: 250033003
Sensory ataxic gait (finding)	SCTID: 250029005
Staggering gait (finding)	SCTID: 78691002
Vestibular ataxic gait (finding)	SCTID: 250032008
Spastic gait (finding)	SCTID: 9447003
Paraplegic gait (finding)	SCTID: 250035005
On examination - gait spastic (finding)	SCTID: 163685000
On examination - limping gait (finding)	SCTID: 163691003
Investigations	
ECG PR Prolonged	
Electrocardiogram: partial atrioventricular block - long PR (finding)	SCTID: 164902006
Prolonged PR interval (finding)	SCTID: 164947007
Injury, poisoning and procedural complications	
Injection site discomfort	
Injection site burning (disorder)	SCTID: 95389008
Injection site reaction (disorder)	SCTID: 95377006
Injection site disorder (disorder)	SCTID: 95376002

Table 3 SNOMED-CT concepts for the study	
Study outcome	SNOMED code
Injection site dermatitis (disorder)	SCTID: 95393002
Injection site urticaria (disorder)	SCTID: 95394008
Injection site edema (disorder)	SCTID: 95392007
Swelling at injection site (disorder)	SCTID: 213340005
Injection site inflammation (disorder)	SCTID: 95391000
Injection site induration (disorder)	SCTID: 95402002
Induration at injection site (disorder)	SCTID: 213337005
Injection site hypersensitivity (disorder)	SCTID: 95378001
Injection site cyst (disorder)	SCTID: 95396005
Injection site mass (disorder)	SCTID: 95395009
Injection site ulcer (disorder)	SCTID: 95400005
Injection site abscess (disorder)	SCTID: 95382004
Injection site atrophy (disorder)	SCTID: 95404001
Injection site necrosis (disorder)	SCTID: 95397001
Injection site fibrosis (disorder)	SCTID: 95403007
Injection site bruising (disorder)	SCTID: 95401009
Injection site infection (disorder)	SCTID: 95381006
Injection site granuloma (morphologic abnormality)	SCTID: 24389009
Injection site thrombosis (disorder)	SCTID: 95386001
Injection site hemorrhage (disorder)	SCTID: 95385002
Injection site paresthesia (disorder)	SCTID: 95399003
Injection site nerve damage (disorder)	SCTID: 95390004
Injection site malabsorption (disorder)	SCTID: 95387005
Injection site extravasation (disorder)	SCTID: 95384003
On examination - Injection sites abnormal (disorder)	SCTID: 308092004
Injection site sterile abscess (disorder)	SCTID: 95383009
Injection site pigmentation change (disorder)	SCTID: 95380007
Application AND/OR injection site disorder	SCTID: 95363008
Application site rash (disorder)	SCTID: 95371007
Injection site pain (disorder)	SCTID: 95388000
Erythema at injection site (disorder)	SCTID: 213338000
Injection site irritation (disorder)	SCTID: 95379009
Injection site erythema	
Erythema at injection site (disorder)	SCTID: 213338000
Injection site irritation	
Injection site irritation (disorder)	SCTID: 95379009
Injection site pain	
Injection site pain (disorder)	SCTID: 95388000

Table 3 SNOMED-CT concepts for the study	
Study outcome	SNOMED code
Psychiatric disorders	
Abnormal behavior (finding)	SCTID: 25786006
Mildly abnormal behavior (finding)	SCTID: 165311008
Severely abnormal behavior (finding)	SCTID: 165312001
Drug reaction with eosinophilia and systemic symptoms Syndrome	
Drug reaction with eosinophilia and systemic symptoms Syndrome (disorder)	SCTID: 702809001
Acute generalized exanthematous pustulosis (disorder)	SCTID: 702617007
Severe cutaneous adverse reactions	
Drug reaction with eosinophilia and systemic symptoms Syndrome (disorder)	SCTID: 702809001
Acute generalized exanthematous pustulosis (disorder)	SCTID: 702617007
Lyell syndrome (disorder)	SCTID: 768962006
Toxic epidermal necrolysis caused by drug (disorder)	SCTID: 402744003
Stevens-Johnson syndrome, toxic epidermal necrolysis spectrum (disorder)	SCTID: 768946000
Stevens Johnson syndrome AND toxic epidermal necrolysis overlap (disorder)	SCTID: 124911000119100
Stevens-Johnson and toxic epidermal necrolysis overlap syndrome caused by drug (disorder)	SCTID: 724833000
Stevens-Johnson syndrome (disorder)	SCTID: 73442001
Stevens-Johnson syndrome caused by drug (disorder)	SCTID: 403609001
Cutaneous hypersensitivity (disorder)	SCTID: 21626009
Hypersensitivity	
Non-allergic drug hypersensitivity disorder (disorder)	SCTID: 427640001
Hypersensitivity disease of liver caused by drug (disorder)	SCTID: 735456000
Renal hypersensitivity caused by drug (disorder)	
Allergic reaction, caused by correct medicinal substance properly administered (disorder)	SCTID: 762531008
	SCTID: 57302007
Drug reaction with symptoms ( eosinophilia and systemic disorder)	SCTID: 702809001

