### **5.5.2 Secondary outcome measure**

The secondary variables that will be evaluated in this study include:

- Incidence rate and incidence rate ratio of atrioventricular block
- incidence rate and incidence rate ratio of atrioventricular block complete
- incidence rate and incidence rate ratio of atrioventricular block first degree
- incidence rate and incidence rate ratio of atrioventricular block second degree
- incidence rate and incidence rate ratio of arrhythmia
- incidence rate and incidence rate ratio of bradyarrhythmia
- incidence rate and incidence rate ratio of bradycardia
- incidence rate and incidence rate ratio of cardiac fibrillation
- incidence rate and incidence rate ratio of cardiac flutter
- incidence rate and incidence rate ratio of tachyarrhythmia
- incidence rate and incidence rate ratio of atrial fibrillation
- incidence rate and incidence rate ratio of atrial flutter
- incidence rate and incidence rate ratio of cardiac arrest
- incidence rate and incidence rate ratio of torsade de pointes
- incidence rate and incidence rate ratio of ventricular arrhythmia
- incidence rate and incidence rate ratio of ventricular fibrillation
- incidence rate and incidence rate ratio of ventricular tachyarrhythmia
- incidence rate and incidence rate ratio of palpitations
- incidence rate and incidence rate ratio of chest pain
- incidence rate and incidence rate ratio of gait disturbances
- incidence rate and incidence rate ratio of injection site discomfort
- incidence rate and incidence rate ratio of injection site erythema
- incidence rate and incidence rate ratio of injection site irritation
- incidence rate and incidence rate ratio of injection site pain
- incidence rate and incidence rate ratio of stevens-johnson syndrome
- incidence rate and incidence rate ratio of toxic epidermal necrolysis
- incidence rate and incidence rate ratio of angioedema
- incidence rate and incidence rate ratio of urticaria

- incidence rate and incidence rate ratio of pruritus
- incidence rate and incidence rate ratio of rash
- incidence rate and incidence rate ratio of dizziness
- incidence rate and incidence rate ratio of somnolence
- incidence rate and incidence rate ratio of paresthesias
- incidence rate and incidence rate ratio of loss of consciousness
- incidence rate and incidence rate ratio of syncope
- incidence rate and incidence rate ratio of appetite disorder
- incidence rate and incidence rate ratio of decreased appetite

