  - Cardiac flutter
  - Tachyarrhythmia
  - Atrial fibrillation
  - Atrial flutter
  - Cardiac arrest

- 
- Torsade de pointes
  - Ventricular arrhythmia
  - Ventricular fibrillation
  - Ventricular tachyarrhythmia
  - Palpitations
  - Skin and subcutaneous tissue disorders
    - Stevens-Johnson syndrome
    - Toxic epidermal necrolysis
    - Angioedema
    - Urticaria
    - Pruritus
    - Rash
  - Nervous system disorders
    - Dizziness
    - Somnolence
    - Paresthesias
    - Loss of consciousness
    - Syncope
  - Metabolism and nutrition disorders
    - Appetite disorder
    - Decreased appetite
    - Diet refusal
    - Hypophagia
    - Food aversion
  - General disorders and administration site conditions
    - Chest pain
    - Gait disturbances
  - Injury, poisoning and procedural complication
    - Injection site discomfort
    - Injection site erythema
    - Injection site irritation
    - Injection site pain

Table 3 SNOMED-CT concepts for the study	
Study outcome	SNOMED code
Cardiac Disorders	
Atrioventricular block	SCTID: 233917008
Atrioventricular block complete	SCTID: 27885002
Atrioventricular block first degree	SCTID: 270492004
Atrioventricular block second degree	SCTID: 195042002
Cardiac Arrhythmia (disorder)	SCTID: 698247007
Nodal rhythm disorder (disorder)	SCTID: 71792006
Atrial arrhythmia (disorder)	SCTID: 17366009
Cardiac arrhythmia (disorder)	SCTID: 698247007
Atrio-ventricular node arrhythmia (disorder)	SCTID: 88412007
Neonatal dysrhythmia (disorder)	SCTID: 276513001
Electrocardiogram: sinus arrhythmia (finding)	SCTID: 427393009
Ventricular arrhythmia (disorder)	SCTID: 44103008
Premature beats (disorder)	SCTID: 29717002
Electrocardiographic ventricular arrhythmia (finding)	SCTID: 164893009
Supraventricular arrhythmia (disorder)	SCTID: 72654001
Electrocardiographic supraventricular arrhythmia (finding)	SCTID: 164887001
Bradyarrhythmia	SCTID: 421869004
Supraventricular bradyarrhythmia (disorder)	SCTID: 762534000
Bradycardia	
Electrocardiogram: bradycardia (finding)	SCTID: 426627000
Bradycardia (finding)	SCTID: 48867003
Cardiac fibrillation (disorder)	SCTID: 40593004
Ventricular fibrillation (disorder)	SCTID: 71908006
Atrial fibrillation (disorder)	SCTID: 49436004
Rapid atrial fibrillation (disorder)	SCTID: 314208002
Electrocardiographic atrial fibrillation (finding)	SCTID: 164889003

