Electrocardiographic ventricular fibrillation (finding)	SCTID: 164896001
Chronic atrial fibrillation (disorder)	SCTID: 426749004
Paroxysmal atrial fibrillation (disorder)	SCTID: 282825002
Persistent atrial fibrillation (disorder)	SCTID: 440059007
Preexcited atrial fibrillation (disorder)	SCTID: 762247006
Atrial fibrillation and flutter (disorder)	SCTID: 195080001
Non-rheumatic atrial fibrillation (disorder)	SCTID: 233911009
Sustained ventricular fibrillation (disorder)	SCTID: 429243003
Lone atrial fibrillation (disorder)	SCTID: 233910005
Ventricular fibrillation and flutter (disorder)	SCTID: 195083004
Permanent atrial fibrillation (disorder)	SCTID: 440028005

Table 3 SNOMED-CT concepts for the study	
Study outcome	SNOMED code
Cardiac flutter	
Fluttering heart (finding) *	SCTID: 161969004
Ventricular fibrillation and flutter (disorder)	SCTID: 195083004
Atrial fibrillation and flutter (disorder)	SCTID: 195080001
Tachyarrhythmia (disorder)	SCTID: 6285003
Atrial fibrillation	SCTID: 49436004
Atrial fibrillation and flutter (disorder)	SCTID: 195080001
Paroxysmal atrial fibrillation (disorder)	SCTID: 282825002
Rapid atrial fibrillation (disorder)	SCTID: 314208002
Electrocardiographic atrial fibrillation (finding)	SCTID: 164889003
Chronic atrial fibrillation (disorder)	SCTID: 426749004
Persistent atrial fibrillation (disorder)	SCTID: 440059007
Preexcited atrial fibrillation (disorder)	SCTID: 762247006
Atrial fibrillation and flutter (disorder)	SCTID: 195080001
Non-rheumatic atrial fibrillation (disorder)	SCTID: 233911009
Lone atrial fibrillation (disorder)	SCTID: 233910005
Ventricular fibrillation and flutter (disorder)	SCTID: 195083004
Permanent atrial fibrillation (disorder)	SCTID: 440028005
Atrial flutter	SCTID: 5370000
Electrocardiographic atrial flutter (finding)	SCTID: 164890007
Typical atrial flutter (disorder)	SCTID: 720448006
Atypical atrial flutter (disorder)	SCTID: 15964901000119107
Cardiac arrest	SCTID: 410429000
Neonatal cardiac arrest (disorder)	SCTID: 180906006
Bradycardic cardiac arrest (disorder)	SCTID: 703162001
Cardiac arrest due to cardiac disorder (disorder)	SCTID: 423191000
Torsade de pointes	SCTID: 31722008
Electrocardiographic torsades de pointes (finding)	SCTID: 426882006
Ventricular arrhythmia	SCTID: 44103008
Electrocardiographic ventricular arrhythmia (finding)	SCTID: 164893009
Ventricular fibrillation	SCTID: 71908006

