Electrocardiographic ventricular fibrillation (finding)	SCTID: 164896001
Sustained ventricular fibrillation (disorder)	SCTID: 429243003
History of ventricular fibrillation (situation)	SCTID: 161513002
Ventricular tachyarrhythmia (disorder)	SCTID: 6624005
Palpitations (finding)	SCTID: 80313002
Palpitations - rapid (finding)	SCTID: 248648003
Bumping heart (finding)	SCTID: 161968007

Table 3 SNOMED-CT concepts for the study	
Study outcome	SNOMED code
Pounding heart (finding)	SCTID: 248657009
Fluttering heart (finding) *	SCTID: 161969004
Palpitations with regular rhythm (finding)	SCTID: 428919002
Intermittent palpitations (finding)	SCTID: 102590007
History of palpitations (situation)	SCTID: 473122004
Skin and subcutaneous tissue disorders	
Stevens-Johnson syndrome (disorder)	SCTID: 73442001
Stevens-Johnson syndrome caused by drug (disorder)	SCTID: 403609001
Stevens-Johnson syndrome, toxic epidermal necrolysis spectrum (disorder)	SCTID: 768946000
Stevens Johnson syndrome AND toxic epidermal necrolysis overlap (disorder)	SCTID: 124911000119100
Stevens-Johnson and toxic epidermal necrolysis overlap syndrome caused by drug (disorder)	SCTID: 724833000
Toxic epidermal necrolysis	
Lyell syndrome (disorder)	SCTID: 768962006
Toxic epidermal necrolysis caused by drug (disorder)	SCTID: 402744003
Stevens-Johnson syndrome, toxic epidermal necrolysis spectrum (disorder)	SCTID: 768946000
Stevens Johnson syndrome AND toxic epidermal necrolysis overlap (disorder)	SCTID: 124911000119100
Stevens-Johnson and toxic epidermal necrolysis overlap syndrome caused by drug (disorder)	SCTID: 724833000
Angioedema	SCTID: 41291007
Giant urticaria (disorder)	SCTID: 400075008
Drug-aggravated angioedema-urticaria (disorder)*	SCTID: 241958006
Angioedema and/or urticaria (disorder)*	SCTID: 404177007
Urticaria	SCTID: 126485001
Acute urticaria (disorder)	SCTID: 402408009
Chronic urticaria (disorder)	SCTID: 51611005
Allergic urticaria (disorder)	SCTID: 40178009
Immunologic urticaria (disorder)	SCTID: 40370006
Contact urticaria (disorder)	SCTID: 19364004
Allergic contact urticaria (disorder)	SCTID: 402304007
Urticaria medicamentosa (disorder)	SCTID: 11012891000119106
Urticaria caused by serum (disorder)	SCTID: 89322006
Drug-aggravated angioedema-urticaria (disorder)*	SCTID: 241958006
Angioedema and/or urticaria (disorder)*	SCTID: 404177007

Table 3 SNOMED-CT concepts for the study	
Study outcome	SNOMED code

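### Table 3 rolls subtype codes up into cardiac fibrillation but not into AV block or cardiac flutter, so some parent outcomes omit their own subtypes

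*Protocol*

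**What the plan says.** Section 5.5.2 of the protocol lists the secondary outcomes at one level, each with its own rate and rate ratio. The first is "Incidence rate and incidence rate ratio of atrioventricular block". Complete, first-degree and second-degree block follow as separate entries, and cardiac flutter and atrial flutter are also separate entries. Under 5.9.1.2 the numerator is the number of patients with the outcome, and person-time runs to the first occurrence of that outcome.

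Table 3 in 5.5.5 is the only code list the protocol supplies. Its cardiac block reads as follows:

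- Atrioventricular block has the single code "SCTID: 233917008". Complete block is "SCTID: 27885002", first-degree block "SCTID: 270492004" and second-degree block "SCTID: 195042002", each on its own line.
- The outcome whose heading begins "Cardiac fibrillation (disorder" is followed by atrial and ventricular fibrillation codes that also appear under their own outcomes.
- Cardiac flutter has no code on its heading row. Beneath it are fluttering heart and the two combined fibrillation-and-flutter codes.
- Atrial flutter has four codes, none of them shown under cardiac flutter.

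Section 5.5.5 also says that the listed concepts will be reviewed and that case definitions will be developed with clinicians. It describes SNOMED-CT as hierarchical. It does not say that a listed code brings in its descendants, or that a broader outcome counts the narrower ones.

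**The concern.** A reader who sees a rate for AV block, followed by rates for its three degrees, will take the first as any AV block. By the listed codes it is only block recorded under the general code. A reader of the cardiac fibrillation line, by contrast, does get nearly all the fibrillation subtypes. The two lines look alike in a results table but are built differently, and nothing in the protocol says so.

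The cost falls on the secondary dose comparison. Section 5.9.3 expects several hundred patients after the criteria are applied, so individual cardiac events may well be few. A dose-related excess of graded block would then be spread over three lines and absent from the line a reader checks first. A broader outcome reported below its own subtype would also look like a programming error.

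**Working it through.** No sample size, power or alpha is involved, and the plan gives no figure to reproduce. The check compares code sets.

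**Inputs.** These are the distinct SNOMED-CT codes under each cardiac heading of Table 3, with repeated rows counted once.

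**Test.** For each broader outcome P and narrower outcome S, count how many codes of S are also listed under P.

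| Broader outcome (codes listed) | Narrower outcome | Codes of S found in P |
|---|---|---|
| Cardiac fibrillation (16) | Atrial fibrillation | 12 of 12 |
| Cardiac fibrillation (16) | Ventricular fibrillation | 3 of 4 (the history code 161513002 is missing) |
| Arrhythmia (11) | Ventricular arrhythmia | 2 of 2 |
| Atrioventricular block (1) | Complete / first / second degree | 0 of 1 / 0 of 1 / 0 of 1 |
| Cardiac flutter (3) | Atrial flutter | 0 of 4 |
| Ventricular arrhythmia (2) | Ventricular fibrillation / torsade / ventricular tachyarrhythmia | 0 of 4 / 0 of 2 / 0 of 1 |
| Arrhythmia (11) | Atrial fibrillation / atrial flutter / ventricular fibrillation | 0 of 12 / 0 of 4 / 0 of 4 |
| Arrhythmia (11) | Bradyarrhythmia / tachyarrhythmia | 0 of 2 / 0 of 1 |

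The four atrial flutter codes missing from cardiac flutter are 5370000, 164890007, 720448006 and 15964901000119107. The one ventricular tachyarrhythmia code missing from ventricular arrhythmia is "SCTID: 6624005".

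**Which convention the table follows.** The first three rows show subtypes written out under a broader outcome. The same happens outside the cardiac block. Injection site discomfort repeats the codes for injection site pain (95388000), erythema (213338000) and irritation (95379009), and appetite disorder repeats the code for decreased appetite (64379006). The remaining rows show the opposite. Arrhythmia does both within one list.

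**A separate misplacement.** Code 195083004, ventricular fibrillation and flutter, appears under cardiac fibrillation, cardiac flutter and atrial fibrillation, but not under ventricular fibrillation. It is out of place under either convention.

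**Effect on rates.** Write N for patients with the outcome and T for patient-days to first occurrence or censoring.

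- If the list for P contains the list for S, every S case is a P case, so N(P) ≥ N(S). Follow-up for P stops no later than for S, so T(P) ≤ T(S). Hence N(P)/T(P) ≥ N(S)/T(S), and a broader rate cannot fall below a narrower one.
- If the lists share no code, as for AV block and its degrees, neither inequality is guaranteed. The AV block rate can then be lower than the rate of any one degree, including zero when a degree has cases.

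This ordering applies to rates within a cohort. It does not order the rate ratios. The rate ratio for AV block would simply compare a different and narrower event from the one its label suggests.

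**After a roll-up.** AV block goes from 1 to 1 + 3 = 4 codes and cardiac flutter from 3 to 3 + 4 = 7. Moving 195083004 takes atrial fibrillation from 12 to 11 codes and ventricular fibrillation from 4 to 5. Cardiac fibrillation stays at 16 and then holds every ventricular fibrillation code except the history code.

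**The case against.** The strongest reply is that Table 3 is a starting list. Section 5.5.5 sends it to clinical review, 5.4.1 leaves the hierarchical level of final reporting to be agreed with the sponsor's safety physicians, and 5.7.1 says code-set development takes terminology structure into account. An SAP or code-set specification that is not at hand may settle the matter. This stands in part. It means the error is conditional on querying by the listed codes. It does not remove the inconsistency, because none of these sections states a roll-up or descendant rule.

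A second reply is that SNOMED-CT retrieval may include descendants automatically. The protocol never says so, and automatic inclusion would make much of the listing under cardiac fibrillation redundant. It might repair AV block. Whether it would repair cardiac flutter, which has no heading code, cannot be told from the documents.

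A third reply is that 5.5.1 speaks of selected preferred terms, so term-by-term counting may be intended. That is a legitimate convention, but the subtype codes repeated under cardiac fibrillation, arrhythmia and injection site discomfort then contradict it.

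Chart review and sensitivity analyses do not settle the point either. Section 5.1 plans chart review of all eligible patients and 5.4.1 of about 10%, and neither says how a graded block maps to the broader outcome. The one outcome-definition sensitivity analysis specified in 5.9.1.4 adds a related medication or procedure code, which cannot restore diagnosis codes left off a list.

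A reader might infer that graded block is lost from the study. The documents do not support that. Each degree has its own rate and rate ratio, and all of them count in the cardiac category if it pools the listed codes.

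**Conclusion.** The point holds as an inconsistency in a stated code list for secondary safety outcomes. The firm findings are that 0 of 3 graded-block codes are under AV block, that 0 of 4 atrial flutter codes are under cardiac flutter, and that 195083004 is listed under atrial but not ventricular fibrillation. Queried by the listed codes, the affected broader outcomes omit their own subtypes and their rates can fall below them. Arrhythmia and ventricular arrhythmia have the same gap.

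The conclusion rests on two conditions: that outcomes are retrieved by the codes listed, and that no descendant rule is set elsewhere. The pooled cardiac rate is unaffected provided it counts all listed cardiac codes.

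A reader might also want a percentage by which the AV block rate is understated. None can be given, because the protocol says nothing on how often block is coded without a grade in this database. The bradyarrhythmia and tachyarrhythmia lines are less clear. Whether bradycardia, for example, belongs under bradyarrhythmia is a clinical and terminology judgement the documents do not make. The point is worth correcting before programming, but it does not threaten the primary objective.

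**What to change.** State one rule in 5.5.5 on whether a broader outcome counts its listed subtypes and their SNOMED-CT descendants, and make Table 3 conform.

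Under a roll-up rule:

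- Add 27885002, 270492004 and 195042002 to atrioventricular block.
- Add 5370000, 164890007, 720448006 and 15964901000119107 to cardiac flutter.
- Move 195083004 from atrial fibrillation to ventricular fibrillation.
- Apply the same rule to arrhythmia and ventricular arrhythmia.
- Leave history codes such as 161513002 out of the roll-up. Table 3 already marks the history codes for urticaria and angina as prevalent, and they do not describe a new event.
- Send the membership of bradyarrhythmia and tachyarrhythmia to the clinician review that 5.5.5 already plans.
- Program a check, within each cohort and with history codes set aside, that no broader outcome has fewer patients than any of its subtypes.

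If term-by-term counting is preferred, remove the repeated subtype codes from the broader outcomes, label the AV block line as block without a recorded degree, and still correct the placement of 195083004.

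The cost is an edit to the code list and one added check. No new data are needed, and the pooled cardiac rate does not change if it already counts every listed cardiac code.
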